11.1 Baseline Assessments

The baseline assessments will be performed immediately following screening for phase 3 criteria. The following measures will be assessed at the baseline visit.

- Baseline Weight, Height, and Body Mass Index*
- Demographics and Blood Draw Information*
- Modified Mini-Mental State Examination*
- Six-Minute Walk Test*
- Baseline Interview
- Activities-Specific Balance Confidence†
- Short Physical Performance Battery
- SF-36 Health Survey†
- Modified Physical Performance Test
- Yale Physical Activity Survey†
- Weight and Quadriceps Strength†
- Center for Epidemiologic Studies-Depression scale
- Pepper Assessment Tool for Disability†
- Mini Nutritional Assessment-Short Form
- Life Orientation Test-Revised
- Brief Resilience Scale

* Collected as part of phase 3 screening

† Eliminated from baseline assessment in protocol version 11.0

11.2 Follow-up Assessment

The following measures will be obtained at 16 weeks post-randomization.

- Six-Minute Walk Test
- Modified Mini-Mental State Examination[†]
- Activities-specific Balance Confidence[†]
- Short Physical Performance Battery
- SF-36 Health Survey[†]
- Modified Physical Performance Test
- Yale Physical Activity Survey[†]
- Weight and Quadriceps Strength[†]
- Center for Epidemiologic Studies-Depression scale
- Pepper Assessment Tool for Disability[†]
- Mini Nutritional Assessment-Short Form[^]

[†] Eliminated from follow-up assessment in protocol version 11.0

[^] Eliminated from follow-up assessment in protocol version 12.0

Note: The subset of participants randomized prior to protocol version 10.0 received a second follow-up assessment at 40 weeks post-randomization using the complete list of measures above.

11.3 Telephone Interviews

Structured telephone interviews with blinded assessors will be conducted every four weeks for 16 weeks post-randomization starting four weeks after the date of randomization. Participants will be given a health diary at the baseline visit to assist with recall during the telephone interviews. The following measures will be administered:

- Reportable Adverse Events (RAE) Form
- Health Care Utilization questionnaire[†]
- Expected Adverse Events (AE) Form
- Self-report of study medication adherence[†]

[†] Eliminated from telephone interview in protocol version 11.0

Note: The subset of participants enrolled prior to protocol version 10.0 received telephone calls every four weeks for 40 weeks post-randomization using all the measures listed above.

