9.6 Scheduling Intervention Visits

There are three requirements for scheduling of intervention visits:

1. The first intervention visit should occur on Day 7 or earlier, where the day of randomization = Day 0.
2. The schedule of intervention visits is anchored to the date of randomization regardless of when the intervention starts.
3. Intervention visits should never occur on two consecutive days, even when moving from one week to the next.

For all randomized participants, Week 1 will begin on the day of the first intervention visit or on Day 7 post-randomization, whichever is earlier. Subsequent weeks will start on the same day of the week as Week 1. For example, if the participant's first intervention visit is on a Wednesday, each intervention week for that participant will extend from Wednesday to Tuesday (inclusively). Alternatively, if the first visit has not yet occurred by Day 7 and Day 7 is a Monday, then the participant's intervention weeks will extend from Monday to Sunday (inclusively).

In certain circumstances (e.g., illness, travel), the first intervention visit may be scheduled after Day 7.

Ideally participants will receive 2 visits per week for 16 weeks post-randomization (32 visits total). However, missed visits in a given week can be replaced by makeup visits in subsequent weeks (not to exceed 3 visits in any given week) as long as the visits are on non-consecutive days. If the participant has not had 32 visits by the end of 16 weeks, makeup visits can be performed during the subsequent two weeks to get as close as possible to the target of 32 visits.

Section 10: Study Measures

A list of study measures is provided below. All of the measures will be interview-based or based on observations of performance or physiological assessments. No proxy data will be allowed at baseline. However, at the 16-week follow-up visit, a proxy may be contacted to provide information about the participant's walking ability. This information will be used as part of the adjudication process, as described in section 11.5. Also, the four-week phone calls will be conducted with a proxy when the participant is not available.

In the description of measures below, we identify the measures that will not be collected for participants consented under protocol version 11.0 or later.

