10.6.3 Reportable Adverse Events (RAEs)

Reportable adverse events (RAEs), which include serious adverse events (SAEs), unexpected AEs or injury that occurs under supervision by study staff, will also be obtained during the study. These events will be tracked in a separate database by the CCC. RAEs will be captured every four weeks during the telephone interviews using standardized questions on the Reportable Adverse Events Form. Participants (or their proxies) will be asked about life-threatening or significant medical events and the outcomes of these events. RAEs will also be asked about by study staff prior to each PT visit and clinical site follow-up assessment. RAEs may be spontaneously reported to any study staff member throughout the study (see section 13.4.1).

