10.6.4 Expected Adverse Events (AEs)

Expected AEs will be assessed every four weeks during the telephone interview. Participants (or their proxies) will be asked a series of standardized questions related to pain (feet, hip, back, knees); breathing problems or chest pain; skin irritations, rash, or skin tears; numbness or tingling; and falls (with and without injury).

Section 11: Study Procedures

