13.4.1 Serious Adverse Event (SAE)

SAEs will be defined as any event that:

- Results in death
- Is life threatening, or places the participant at immediate risk of death (e.g., MI, stroke/TIA)

- Requires or prolongs hospitalization
- Causes significant disability or incapacity (e.g., torn muscle or ligament)
- Requires medical or surgical intervention to prevent significant disability (e.g., hip fracture)

SAEs will be captured through telephone interviews every four weeks by blinded personnel, using the Reportable Adverse Events Form. SAEs will also be assessed at the beginning of each PT visit and clinical site follow-up visit, and by any study staff who learns of a serious event.

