13.5 Expected AE and RAE Collection and Reporting

The requirements for reporting RAEs will begin when the participant provides informed consent and will end 30 days after the participant's involvement in the study has ended. Expected AEs will be assessed every four weeks post-randomization. Figures 5a-d provide algorithms describing the reporting process.

Figure 5a. Collection and Reporting Process for Expected AEs

[figure not shown]

Figure 5b. Collection and Reporting Process for RAEs Collected during Standardized Telephone Interviews

Blinded evaluator administers the Reportable Adverse Events Form at a scheduled 4-week telephone interview

Event is identified by the participant or proxy & meets the criteria for an RAE

Blinded evaluator completes a Reportable Adverse Event Record for each event and submits documentation to the clinical site coordinator

Has the RAE been previously reported?

Clinical site coordinator records RAE ID#, marks as duplicate, and files in participant binder

Clinical site coordinator assigns new RAE ID#, and records event on the RAE Log in the participant binder

Clinical site coordinator notifies clinical site PI and clinical site clinician immediately

Clinical site PI (or designee) redacts documents to conceal treatment assignment and notifies the CCC in writing (by fax or email) within 24 hours of the event being reported to the PI

CCC NOTIFIES DSMB AND NIA IN WRITING (BY FAX OR EMAIL) WITHIN 24 HOURS OF THE EVENT BEING REPORTED TO THE CCC

LEGEND

Clinical Site Staff

Site Coordinator

CCC

Figure 5c. Collection and Reporting Process for RAEs Identified Anytime Other than During a Standardized Telephone Interview

[figure not shown]
[figure not shown]

Figure 5d. CCC Reporting Process for RAEs

Timeline for Reporting Events

The RAE reporting schedule is shown below:

1. RAEs will be reported to the clinical site PI and clinical site clinician as soon as the event is known.
2. The clinical site PI (or designee) will redact documents to conceal treatment assignment and report all RAEs to the CCC in writing (by fax or email) within 24 hours of the event being reported to the investigator.
3. The CCC will report all RAEs to the DSMB and NIA in writing (by fax or email) within 24 hours of being notified.
4. The DSMB and NIA will receive notification about all RAEs within 48 hours of when the event is known and reported by study staff.

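### For participants on the 16-week schedule, the last interview that collects expected adverse events can come before the last treatment visits, and no rule ties the two together.

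*Protocol*

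**What the plan says.** Four parts of the protocol bear on this.

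- **Calls.** Section 11.3: "Structured telephone interviews with blinded assessors will be conducted every four weeks for 16 weeks post-randomization". Table 1 (11.4) gives each call a window of one week before to three weeks after its target. Participants from before version 10.0 were called every four weeks to week 40. Section 1 ends all follow-up at 16 weeks for those consented under version 10.0.
- **Expected AEs.** Section 10.6.4: "Expected AEs will be assessed every four weeks during the telephone interview". Section 13.3 names the same route and lists pain at four sites, breathing problems, chest pain, skin problems, numbness or tingling, and falls. The list of follow-up measures in 11.2 contains no expected-AE form.
- **Treatment visits.** Section 9.6: "Week 1 will begin on the day of the first intervention visit or on Day 7 post-randomization, whichever is earlier". For participants still short of 32 once the regular schedule is over, "makeup visits can be performed during the subsequent two weeks to get as close as possible to the target of 32 visits".
- **Reportable and serious AEs.** Section 10.6.3: "RAEs will also be asked about by study staff prior to each PT visit and clinical site follow-up assessment". Section 13.4.1 repeats this for serious events: "SAEs will also be assessed at the beginning of each PT visit and clinical site follow-up visit".

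No section requires the final call to come after the last intervention visit.

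**The concern.** The call schedule and the visit schedule end at different times. When calls ran to week 40, this did not matter, because a later call always followed the end of treatment. Version 10.0 removed the later calls, and 11.3 and Table 1 were not adjusted to the makeup period that 9.6 allows.

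Two things are at stake for a participant whose visits continue after the last call. First, a non-serious fall at home, or new hip or knee pain, in that period has no scheduled route into the standardised expected-AE data. Such events are listed as expected and would not normally qualify as reportable. The DSMB reviews these data in tabulated form (13.8). Second, the blinded telephone enquiry about reportable events has also stopped. What remains is the question put by the PTs, who are unblinded (6.4), and the question at the follow-up assessment.

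**Working it through.** All days count from randomization as Day 0.

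**Check of the plan's own counts.** Calls over 40 weeks: 40 / 4 = 10, as stated in Section 1. Visits: 2 per week × 16 weeks = 32, as stated in 9.1. The 16-week schedule has 16 / 4 = 4 calls.

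**Final call (11.3, Table 1).**
- Target: 16 × 7 = Day 112.
- Earliest: 112 − 7 = Day 105.
- Latest: 112 + 21 = Day 133.

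**End of treatment (9.6).** There are two bounding cases.
- Weeks counted from randomization: 16 weeks end on Day 112. Two makeup weeks end on 112 + 14 = Day 126.
- Week 1 starting on Day 7, the latest start that 9.6 allows: 16 weeks end on 7 + 112 − 1 = Day 118. Two makeup weeks end on 118 + 14 = Day 132.

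**Days of permitted treatment after the last call (end of treatment minus call day).**

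| Final call | No makeup weeks (Day 112 to 118) | Both makeup weeks used (Day 126 to 132) |
|---|---|---|
| Day 105, earliest | 7 to 13 | 21 to 27 |
| Day 112, on target | 0 to 6 | 14 to 20 |
| Day 133, latest | none | none |

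**Participants from before version 10.0.** Their week-20 call has target Day 140 and window 140 − 7 = Day 133 to 140 + 21 = Day 161. Even the earliest such call falls after Day 132, so the end of treatment was covered.

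**Number on the shortened schedule.** Section 15.6.2 expects about 150 of 210 to have 40-week data, so 210 − 150 = about 60 (60 / 210 = 29%).

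**The case against.** The strongest reply is that the end of treatment is well observed. Reportable and serious events are asked about before every PT visit, makeup visits included, and again at the follow-up assessment, which is done by blinded staff (6.4). Table 3 (12.1.5) requires falls to be reported with an incident report and sets actions for chest pain and new acute pain at intervention visits. The call window also leans late, to Day 133, so the protocol already permits a call after the last visit. The 27-day figure needs the earliest call, the latest start of Week 1 and makeup visits up to the last permitted day, all together.

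Much of this stands. A reader might infer that end-of-treatment events in general go uncollected. The documents do not support that, because the enquiry about reportable and serious events continues. What the reply does not remove is narrower. Neither the PT-visit enquiry nor the Table 3 alerts are the standardised, blinded expected-AE interview, and a window that permits a late call does not require one. An on-target call precedes any makeup visit made after week 16.

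Three further inferences are tempting and should not be drawn.

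- **That version 10.0 left the 30-day reporting period uncovered.** Under 13.5 the reporting requirement "will end 30 days after the participant's involvement in the study has ended", so the clock runs from the end of involvement and not from the last PT visit. Participants called to week 40 had no scheduled contact in the 30 days after their involvement ended either.
- **That about 60 participants have a gap.** That is the number on the shortened schedule. The number still being visited after their last call is not given.
- **That the gap biases the comparison between arms.** Both arms have the same visit and call schedules, and the documents give no missed-visit figures by arm.

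**Conclusion.** The point holds in limited form. For participants consented under version 10.0 or later, permitted treatment can outlast the last expected-AE interview by up to 6 days in the ordinary case (on-target call, no makeup weeks), by 14-20 days with an on-target call and both makeup weeks used, and by 21-27 days at the extreme. In that interval expected events have no scheduled collection, and reportable events are actively sought only by unblinded PTs or at the follow-up assessment.

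This rests on the windows as written in Table 1 and 9.6, on the two ways of counting intervention weeks shown above, and on the protocol's own estimate of about 150 participants followed to week 40. How many of the remaining 60 or so are affected depends on actual call dates and use of makeup visits, which the documents do not report. The primary outcome and its analysis are not touched. This is an inexpensive improvement to safety ascertainment.

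**What to change.** In 11.3 and Table 1, require the fourth and final telephone interview to take place after the participant's last intervention visit, makeup visits included, within the existing three-week late window. Where makeup visits end near Day 132, only about one day of that window is left, so allow this call a few days' extension. State that the call covers the whole period since the previous one.

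No call, form or staff time is added. The cost is recall: moving the call from Day 112 to Day 133 lengthens the final recall period by 21 days, about three weeks, or slightly more with the extension. That is a real drawback for transient symptoms such as numbness or skin irritation. The health diary in 11.3 is meant to aid recall, but 10.3.6 describes it as a record of health care use, so it may help little with symptoms. The change closes the gap up to the last visit. It is not meant to provide contact throughout the 30-day reporting period.

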11.4 Timing of Study Procedures

The target date for completion of the pre-randomization (i.e., screening) assessments will be anchored to the date of admission to the hospital for hip fracture. The target date for completion of all other assessments will be anchored to the date of randomization (see Table 1).

Table 1. Timing of Study Procedures

PROCEDURE	TARGET DATE	ALLOWABLE INTERVAL
Phase 3 screening	As early as possible following admission	Up to 26 weeks post-admission
Baseline assessment	As early as possible following admission	Up to 26 weeks post-admission
Randomization	As early as possible following admission	Up to 26 weeks post-admission
Dietitian consult	1 week post-randomization	+1 week
First intervention visit	1 week post-randomization	+16 weeks
First telephone interview	4 weeks post-randomization	-1 week, +3 weeks
Subsequent telephone interviews	At 4-week intervals from date of randomization	-1 week, +3 weeks
First follow-up assessment	16 weeks post-randomization	+2 weeks
Out-of-window assessment	16 weeks post-randomization	0-16 weeks and 18-38 weeks post-randomization

11.5 Primary Outcome Classification

At baseline, all participants will, by design, be tested at the clinical site. At the follow-up visit, we will attempt to test all participants at the clinical site. When this is not possible, we will attempt to have study staff administer the test in a non-study clinical facility or, failing that, at another non-study location or the participant's home. All cases for which, despite intensive efforts, administration of the SMWT is not possible will be submitted for adjudication. See Figure 4.

Although there is an absence of highly sensitive and specific surrogate measures for the ability to walk ≥ 300 m in six minutes, prior studies suggest that there are factors that are highly predictive of the *inability* to walk at that speed. Therefore, the purpose of the adjudication will be to reduce the number of participants with missing outcomes by identifying treatment failures in cases where the SMWT could not be administered. Based on the adjudication, participants who meet one or more of the following criteria at the follow-up assessment will be classified as treatment failures in the primary analysis for the given follow-up time:

- 1) Participant died
- 2) Participant was too sick, based on adjudicators' review of source documentation, to walk 300 m or more in six minutes
- 3) Gait speed based on SPPB four-meter walk was less than 0.6 m/s (very slow speed incompatible with ability to walk 300 m in six minutes)
- 4) Participant or proxy reports (a) participant limitation in walking several blocks or (b) in walking across a small room without help from another person

[figure not shown]
Criterion 4a is an item from the Activity Limitations section of the SF-36 and was chosen because, in a previous hip fracture study performed by our group, 100% of 27 participants meeting the criterion were unable to walk 300 m or more in six minutes (unpublished data). Also, in that study, 85% of 26 participants who had a missing SMWT reported this level of walking limitation, suggesting that use of this item will allow us to assign a classification to a large proportion of those who were not tested on the SMWT. Criterion 4b is an item from the Pepper Assessment Tool for Disability and was chosen because it has high face validity for predicting treatment failure. To improve our ability to classify the outcome status of participants whose SMWT was not administered, we will make intensive efforts to obtain self- or proxy-

reported information on these two items in person or by telephone, even when other data cannot be collected at the given follow-up time.

There will be three adjudicators, all experts in mobility assessment and the clinical management of older persons. Each adjudication case will be randomly assigned to two of the adjudicators who will independently review all the relevant documents and classify participants as treatment failures or indeterminate. If the two adjudicators disagree on the classification, the case will be discussed in a meeting with the two adjudicators. If there is no consensus after discussion between the two assigned adjudicators, the case will be discussed in a meeting with all three adjudicators. Discrepancies will be resolved by a vote if the three adjudicators cannot reach a consensus. To monitor the adjudication process, an unblinded statistician will calculate, among the cases submitted for adjudication, the outcome of adjudication (proportion classified as failure and indeterminate), by treatment group. The incorporation of adjudication results into the analysis plan is described in Section 15.1.

Cases where the SMWT was administered but not according to protocol (e.g., using a walking course of less than 10 m) will also be submitted for adjudication. The adjudicators will review the description of the circumstances and outcome of the testing as recorded by the evaluator and will judge whether the participant's classification (treatment success or treatment failure) based on the distance walked is valid. If not, the participant will be classified as 'indeterminate'. For simplicity, this part of the process is not depicted in Figure 4.

Figure 4. Classification and Analysis of Primary Outcome

Legend:
 S Treatment success in primary analysis
 (S) Treatment success in secondary analysis
 F Treatment failure in primary analysis
 (F) Treatment failure in secondary analysis
 M Missing in primary analysis
 (M) Missing in secondary analysis
 SPPB Short Physical Performance Battery

Note: This flow chart applies only to follow-up assessments. At baseline, all participants will be tested with the Six-Minute Walk Test.

Section 12: Safety Assessments

12.1 Participant Safety Parameters: Methods and Timing

12.1.1 Pre-Intervention Safety Screening

Potential participants will be excluded during the screening phases if they have cardiovascular diseases or other conditions that would make it unsafe for them to participate in one or both of the study interventions. Information about these conditions will be obtained through chart review, interviews, and consultation with a medical professional familiar with the potential participant (e.g., primary care provider, orthopaedic surgeon). The clinical site study clinician and PI will be responsible for giving permission for potential participants to be randomized, based on thorough review of all eligibility information. In addition, persons who develop chest pain or substantial shortness of breath during the SMWT will be excluded using a protocol to evaluate cardiovascular reserve similar to the one suggested by Gill et al.¹⁹⁹

12.1.2 Safety Considerations for Study Assessments

All study assessments will be done by certified staff who will be trained to perform the tests safely. If, during the SMWT, the SPPB, or the mPPT, a participant reports chest pain, tightness or pressure, significant shortness of breath or difficulty breathing, or feeling faint, lightheaded, or dizzy, the test will be stopped. All research staff who come in contact with study participants will be CPR certified and will be trained to provide immediate care when faced with medical emergencies. Also, institutional and community emergency medical services will be activated if needed.

Table 2 describes a summary of safety alerts and the appropriate action during clinical assessments.

Table 2. Safety Alerts and Actions for Study Assessments

ALERT	ACTION
Resting blood pressure SBP > 145mm Hg or DBP > 90mm Hg	Qualified staff will inform the participant if noted on more than one occasion.
Resting blood pressure SBP > 170mm Hg or SBP < 90mm Hg or DBP > 100mm Hg or DBP < 50mm Hg	Qualified staff will encourage the participant to seek additional follow-up and/or medical evaluation. Physical performance testing will be deferred until consultation with the study clinician.
Resting blood pressure or after SMWT SBP > 185mm Hg or SBP < 90mm Hg or DBP > 110mm Hg or DBP < 50mm Hg	Qualified staff will consult with the study clinician and follow up as needed.
Resting pulse Rate > 120 or < 40 beats/min	Qualified staff will consult with the study clinician and follow up as needed.
Chest pain, dizziness, significant shortness of breath, or severe musculoskeletal pain during the intervention or study assessment.	Qualified staff will consult with the study clinician and follow up as needed.
CES-D Score \geq 27	Qualified staff will talk to the participant and provide a referral for additional follow-up and/or medical evaluation for depression.
Weight loss \geq 2% in four weeks during intervention period	Participant will be referred to the registered dietician for follow-up by telephone.
Weight not obtained at the final PT intervention visit and there is weight loss \geq 5% between baseline and follow-up.	Clinical site PI or clinical site clinician will review participant's weight trajectory, baseline BMI, baseline MNA®-SF score and registered dietician's documentation and, if warranted, will refer the participant to a dietician or medical provider for follow-up of possible poor nutritional status.
Participant expresses desire to commit suicide	Call primary care provider and report findings. Report to clinical site coordinator/study clinician for follow-up and clearance.

